3.6.4.9 Unscheduled Visits

Monitoring the safety of the subject by the investigator may require additional unscheduled visits. The sponsor should be consulted prior to performing assessments or procedures

CONFIDENTIAL

outside the scope of the types of assessments that are performed at scheduled visits (ie, for assessments or procedures other than repeat physical examination, hematology, clinical chemistry, urinalysis, FVIII inhibitor titer, and FVIII:C recovery).

3.7 Screen Failures

Screening evaluations will be used to determine the eligibility of each subject for enrollment. Subjects who fail to meet eligibility criteria at Screening may be rescreened once. Subjects who fail to meet eligibility criteria upon rescreening will be considered screen failures and will not be eligible to participate in the study.

3.8 Interruption of ITI Treatment

Interruptions of ITI treatments should be avoided whenever possible because they could have an adverse effect on the outcome of the ITI. If central venous access is temporarily lost because of line infection, ITI should continue through peripheral veins as long as possible until central venous access can be restored.

3.9 Removal of Subjects

Subjects may withdraw or be withdrawn from the study for the following reasons:

- At their own request or at the request of their legally acceptable representative
- If, in the investigator's opinion, continuation in the study would be detrimental to the subject's well-being
- At the specific request of the sponsor

Also subjects must be withdrawn for the following reasons:

- Subject is determined to be a treatment failure at the completion of 33 months of ITI treatment (Section 3.5.1.2).
- Subject has as a confirmed relapse in the Prophylactic Phase in which there is a concomitant loss of clinical response to FVIII therapy.
- Subject develops an infection with HAV, HBV, HCV, or HIV during the study.
- Subject develops a concomitant disease which, either because of its severity or duration or because it requires a change in treatment, contravenes the condition of the study.
- Subject is noncompliant with the protocol per the investigator's discretion.

In all cases, the reason for withdrawal must be recorded in the eCRF and in the subject's records.

3.10 Premature Termination of Study/Closure of Center

The sponsor, IRB/EC, and regulatory authorities have the right to close this study or a study center, and the investigator/sponsor has the right to close a center at any time, although this should occur only after consultation among involved parties. The IRB/EC must be informed.

Should the study or study center be closed prematurely, all study materials (except documentation that has to remain stored at the study center) must be returned to the sponsor. The investigator will retain all other documents until notification is given by the sponsor for destruction.

A study center can be closed for the following reasons:

- Lack of enrollment
- Noncompliance with the requirements of the study protocol
- Noncompliance with ICH GCP

4 ADVERSE EVENTS

4.1 Warnings and Precautions

For complete information on Alphanate, refer to the Investigator's Brochure.

4.2 Adverse Event Monitoring

Subjects must be carefully monitored for AEs. This monitoring includes clinical and laboratory tests and physical signs. Adverse events should be assessed in terms of their seriousness, severity, and relationship to Alphanate.

4.3 Adverse Event Definitions

4.3.1 Adverse Events

An AE is defined as any untoward medical occurrence in a subject or clinical investigation subject administered a medicinal product or study treatment and which does not necessarily have a causal relationship with this administration. An AE can therefore be any unfavorable and unintended sign (including any abnormal laboratory finding, for example), symptom, or disease temporally associated with the use of a medicinal product, whether or not considered related to the medicinal product.

Any AE that occurs at any time between the time of the signature of the informed consent form (ICF) and the last day of the subject's participation in the clinical trial must be reported and recorded on the AE eCRF entry.

All local infusion-site reactions will be recorded in the eCRF. The subset of local infusion-site reactions where the symptoms/signs lead to infusion interruption or discontinuation, require concomitant medication, or have an impact on the general condition of the subject as judged by the investigator will be considered as AEs.

4.3.2 Suspected Adverse Drug Reactions/Adverse Reactions

All noxious and unintended responses to a medicinal product or study treatment related to any dose should be considered suspected ADRs. The phrase "responses to a medicinal

CONFIDENTIAL

product" means that a causal relationship between a medicinal product or study treatment and an AE is at least a reasonable possibility, that is, the relationship cannot be ruled out. An AR is defined as a suspected ADR with a causal relationship of "definite."

4.3.3 Causality of Adverse Event

The investigator is required to provide a causality assessment for each AE reported to the sponsor. The sponsor will consider the investigator's causality assessment and also provide its own assessment. Assessment of the causal relationship to the study drug will be made according to the following classifications based on Karch et al (18):

- **Definite**: an event that follows a reasonable temporal sequence from administration of the treatment or in which the treatment level has been established in body fluids or tissues, that follows a known response pattern to the suspected treatment, and that is confirmed by improvement on stopping the treatment (dechallenge) and reappearance of the event on repeated exposure (rechallenge)
- **Probable**: an event that follows a reasonable temporal sequence from administration of the treatment, that follows a known response pattern to the suspected treatment, that is confirmed by dechallenge, and that could not be reasonably explained by the known characteristics of the subject's clinical state
- **Possible**: an event that follows a reasonable temporal sequence from administration of the treatment, that follows a known response pattern to the suspected treatment, but that could have been produced by the subject's clinical state or other modes of therapy administered to the subject
- **Doubtful/Unlikely**: an event that follows a reasonable temporal sequence from administration of the treatment, that does not follow a known response pattern to the suspected treatment, but that could not be reasonably explained by the known characteristics of the subject's clinical state
- Unrelated: any event that does not meet the criteria above

The operational tool to decide the AE causal relationship is based on algorithms by Karch et al (19) and Naranjo et al (20).

When an AE is classified assessing causal relationship by the investigator, as "definitive," "probable," "possible," or "doubtful/unlikely," the event will be defined as a suspected ADR. When the causal relationship is labeled "unrelated," then it will be considered that the AE is not imputable to the study treatment and it is not a suspected ADR.

In addition, when a causal relationship between the study treatment and the AE cannot be ruled out by the investigator and/or sponsor, it means that the AE cannot be labeled "unrelated."

For any subject, all AEs that occur at any time from the beginning of Alphanate administration until the final visit of the clinical trial will be considered as treatment-emergent AEs.

4.3.4 Severity of Adverse Event or Suspected Adverse Drug Reaction

Adverse events and suspected ADRs will be classified depending on their severity according to the following definitions:

- Mild: an AE which is well tolerated by the subject, causing minimum degree of malaise and without affecting normal activities
- Moderate: an AE that interferes with the subject's normal activities
- Severe: an AE that prevents the subject from performing their normal activities

Adverse event and suspected ADR severity gradation must be distinguished from AE and suspected ADR seriousness gradation, which is defined according to event consequence. For example, headache can be mild, moderate, or severe but not necessarily serious in all these cases.

The investigator will be responsible for assessing the AE and suspected ADR intensity during the clinical trial, taking into account current criteria included in this section.

4.3.5 Expectedness of Adverse Event or Suspected Adverse Drug Reaction

An AE or suspected ADR is considered "unexpected" if the nature, seriousness, severity, or outcome of the reaction(s) is not consistent with the reference information. The expectedness shall be determined by the sponsor according to the reference document (ie, the Investigator's Brochure) for any serious ADRs (potentially related SAEs) for expedited safety reporting purposes.

4.3.6 Seriousness of Adverse Event or Suspected Adverse Drug Reaction; Serious Adverse Event

An AE or suspected ADR is considered "serious" if, in the view of either the investigator or sponsor, it results in any of the following outcomes:

- Death
- Life-threatening AE

(Life-threatening in the definition of "serious" refers to an event in which the subject was at risk of death at the time of the event; it does not refer to an event which hypothetically might have caused death if it were more severe.)

- In-patient hospitalization (when a patient stays more than 24 hours in hospital) or prolongation of existing hospitalization
- A persistent or significant incapacity or substantial disruption of the ability to conduct normal life functions
- A congenital anomaly/birth defect
- An important medical event (Important medical event in the definition of "serious" refers to those events which may not be immediately life-threatening or result in death or hospitalization but from medical

and scientific judgment may jeopardize the subject or may require medical or surgical intervention to prevent one of the other outcomes listed above.)

Only hospital stays of at least 24 hours in duration are to be considered hospitalizations in the definition of an SAE. The following hospitalizations do not qualify an AE as an SAE:

- Hospitalization or prolongation of hospitalization needed for procedures required by the clinical trial protocol.
- Hospitalization or prolongation of hospitalization as part of a routine procedure followed by the center.
- Hospitalization for a survey visit, annual physicals, or social reasons.
- Elective or preplanned hospitalizations for a pre-existing condition that had not worsened from Baseline (eg, elective or scheduled surgery arranged prior to start of the study).
- Admissions not associated with an AE (eg, social hospitalization for purposes of respite care).

This definition permits either the sponsor or the investigator to decide whether an event is "serious." If either the sponsor or the investigator believes that the event is serious, the event must be considered "serious" and evaluated by the sponsor for expedited reporting.

A distinction should be drawn between serious and severe AEs. The term "severe" is used to describe the intensity (severity) of a specific event; the event itself, however, may be of relative minor medical significance (such as severe headache). This is not the same as "serious," which is defined on subject/event outcome or action criteria usually associated with events that pose a threat to a subject's life or functioning. Seriousness (not severity) is a medical term while severity is a subjective term.

4.3.7 Adverse Event Documentation

All AEs and SAEs occurring after the subject has signed the ICF through the final visit (ie, end of study) must be fully recorded in the subject's eCRF and SAE form (if serious) as well as in the medical record. If no AE has occurred during the study period, this should also be indicated in the eCRF.

It is the responsibility of the investigator to ensure that AEs are appropriately recorded.

At each visit, AEs will be elicited by asking the individual a nonleading question such as, "Do you feel different in any way since the last visit?" Moreover, AEs will also be collected through directly observed events or spontaneously volunteered by the subject. Clearly related signs, symptoms, and abnormal diagnostic procedures should preferably be grouped together and recorded as a single diagnosis or syndrome wherever possible.

The following variables must be recorded on the AE eCRF entry:

- The verbatim term (a diagnosis is preferred)
- Date/time of onset

- Date/time of resolution
- Severity (mild, moderate, severe)
- Causality (unrelated, doubtful/unlikely, possible, probable, definite)
 - Causality assessment will be made only when the AE occurs after the subject has initiated at least one administration of Alphanate. An AE occurring before the subject's exposure to Alphanate will be always labeled as "unrelated."
- Seriousness (yes, no)
- Action taken (with regard to Alphanate)
- Other action (to treat the event)
- Outcome and sequelae (follow-up on AE)

For AEs that occur during Alphanate administration, the infusion rate in effect at the time of onset of the AE, the time of onset of the AE, and the time of AE change materially in intensity and/or resolve will be captured in the eCRF entry.

In addition to the investigator's own description of the AEs, each AE will be coded according to the Medical Dictionary for Regulatory Activities (MedDRA).

For example, a laboratory test abnormality considered clinically relevant, eg, causing the subject to withdraw from the study, requiring treatment or causing apparent clinical manifestations, or judged relevant by the investigator, should be reported as an AE. Each event must be adequately supported by documentation as it appears in the subject's medical or case file.

4.3.8 Events of Special Interest

The following AEs during ITI with Alphanate are of special interest, will be intentionally solicited from the subject or subject's caregiver, and will be reported as related to study drug:

- Central venous access and catheter-related complications for which the device was placed or was used for FVIII administration within the trial (eg, line infections, line thrombosis)
- Infusion-site reactions
- Thromboembolic events
- Hypersensitivity reactions, including anaphylaxis and anaphylactoid reactions

4.3.9 Type and Duration of the Follow-Up of Subjects After Adverse Events

Insofar as is possible, all individuals will be followed up until the AE or suspected ADR has been resolved. If an AE/suspected ADR/SAE is present when the subject has completed the study, the course of the event must be followed until the final outcome is known or the event has been stabilized, no further change is expected, and the investigator decides that no further follow-up is necessary.

4.4 Reporting of Serious Adverse Events

[figure not shown]
4.4.1 Reporting Serious Adverse Event

Any SAE (see Section 4.3.6) that occurs after signing the study ICF through the final visit (ie, end of study) must be expeditiously reported whether or not considered attributable to the study drug. Each SAE must be fully recorded in the subject's eCRF and SAE Report Form.

Serious adverse events will be reported using the designated SAE Report Form. When the investigator becomes aware of an SAE, she/he must submit a completed, signed, and dated SAE Report Form (in English) *within 24 hours* to the sponsor by email/fax. The date of this SAE discovery by the site staff should be documented in the source documents (ie, medical records).

Each SAE must be followed up until resolution or stabilization. After the initial report, all relevant information for SAE follow up, and for the outcome, must also be supplied to the sponsor in a timely manner (within 3 days from its identification or within 24 hours for relevant new information) by means of the SAE Report Form. In addition, the sponsor or contract research organization may request additional information and/or reports.

All SAE Report Forms must be reported by email to:

5 STATISTICAL METHODS AND DETERMINATION OF SAMPLE SIZE

5.1 Statistical and Analytical Plans

Data handling and evaluation procedures will be described in the Statistical Analysis Plan.

5.1.1 Subject Populations for Analysis

The subject populations for analysis include the following:

- The Safety Population includes all subjects who receive any amount of Alphanate.
- The Treated Population includes all subjects who are enrolled and treated for ITI with at least 1 dose of Alphanate. In this study, the Treated Population is the same as the Safety Population; however, for efficacy analyses, the term "Treated Population" will be used.
- The Efficacy Evaluable Population includes all subjects who were determined to have achieved complete immune tolerance, to have achieved partial immune tolerance, or to be

treatment failures based on meeting the protocol-specified definitions of these categories of response.

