To accurately capture the peak inhibitor titer on ITI treatment, subjects will have study center visits at Weeks 2, 4, 6, 8, and monthly thereafter. Additional unscheduled visits for inhibitor titer measurements may occur during the first 3 months of ITI treatment and throughout the trial as deemed necessary by the investigator. Weight will be measured at every study center visit, and dosing will be based on the subject's current weight. Between study center visits when Alphanate will be administered at home by the subject's caregiver, the Alphanate dose will be the same as the dose calculated at the most recent study center visit where weight was measured. Training of caregivers at home may be provided within the first few weeks of initiation of ITI treatment for initial port access and newly implanted devices, upon sponsor approval. Ongoing home health care for IP infusions will be assessed on a case-by-case basis.

Subjects will continue to receive their daily Alphanate dose until the inhibitor assay titer is negative (<0.6 BU) on 2 consecutive assessments and treatment success is confirmed by FVIII:C pharmacokinetic assessments (Section 3.5.1.2), at which time they will enter the 12-month Prophylactic Phase.

All subjects will receive ITI treatment for up to 33 months until they achieve complete immune tolerance (Section 3.5.1.2). Subjects who have achieved partial immune tolerance at the completion of 33 months of ITI treatment will enter the 12-month Prophylactic Phase (that includes the protocol-defined dose tapering). Subjects who do not achieve partial

immune tolerance at the completion of 33 months of ITI treatment will be discontinued as treatment failures.

Prophylactic Phase up to 12 months: Upon confirmation of achieving complete immune tolerance, subjects will enter the 12-month Prophylactic Phase (that includes the protocol-defined dose tapering). Subjects achieving partial immune tolerance at the completion of the 33-month ITI Treatment Phase will enter the 12-month Prophylactic Phase (that includes the protocol-defined dose tapering).

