3.5.1.2 Definition of Complete/Partial Immune Tolerance or Failure

Successful achievement of immune tolerance (complete or partial) and failure of ITI are defined per International Consensus Panel recommendations (7) and are detailed below.

Complete immune tolerance is defined as the subject achieving all of the following:

- Undetectable inhibitor titer (<0.6 BU); must be confirmed by 2 consecutive assessments performed within approximately 2 weeks of each other
- FVIII:C plasma recovery $\geq 66\%$ of the predicted normal value
- FVIII:C half-life ≥6 hours after a 72-hour FVIII treatment-free period

Partial immune tolerance is defined as the subject achieving all of the following:

- Reduction of inhibitor titer to <5 BU; must be confirmed by 2 consecutive assessments performed within approximately 2 weeks of each other
- FVIII:C plasma recovery of <66% of the predicted normal value or FVIII:C half-life of <6 hours after a 72-hour FVIII treatment-free period
- Clinical response to FVIII therapy

Treatment failure is defined as:

• Failure to fulfill the criteria for complete or partial immune tolerance within 33 months

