3.6.3.1 Virus Safety Testing

Blood samples for viral nucleic acid amplification technology (NAT) and viral serology will be collected at Baseline, prior to Alphanate administration, and analyzed for information only. If necessary, in order to minimize total blood volume drawn per day, virus safety samples may be drawn the day prior to the Baseline Visit instead of combining with other baseline blood draws on a single day. Virus safety retain samples will be collected, but only tested if subjects show clinical signs and/or symptoms of viral infection, at the following time points:

- At the Screening Visit
- At the Week 8 Visit of the ITI Treatment Phase
- At the Month 6 Visit of the ITI Treatment Phase
- At the Month 15 Visit of the ITI Treatment Phase
- At the Month 30 Visit of the ITI Treatment Phase
- At the Month 33 Visit of the ITI Treatment Phase (unless a subject achieves complete immune tolerance prior to Month 33, in which case a viral retain sample will be collected at his/her last visit during the ITI Treatment Phase, before entering the Prophylactic Phase)
- At the Early Termination Visit for treatment failures and early withdrawals
- At the last visit of the Prophylactic Phase

Virus safety retain samples will be stored for up to an additional 5 years after all analyses in support of the study are complete. Additional blood samples for viral NAT and viral serology testing may be collected and tested during the study *only* if the subject exhibits clinical signs and symptoms consistent with hepatitis A virus (HAV), HBV, HCV, HIV, or parvovirus B19 (B19V) infection while participating in the study.

Any potential extra serum/plasma samples (refer to Table 3-1, footnote 'b') will be stored for up to an additional 5 years after completion of the study for

No poststudy genetic testing will be performed.

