3.6.4.8 Early Termination Visit

The following assessments and procedures will be performed for subjects who are withdrawn from the study for treatment failure or subjects who discontinue the study prematurely for any reason:

- Adverse events
- Concomitant medications
- Vital signs
- Weight
- Physical examination, excluding genitourinary examination
- Blood and urine samples for clinical laboratory assessments to be sent to the central laboratory
 - Hematology: hemoglobin, hematocrit, platelets, red blood cell count including red blood cell morphology, white blood cell count with differential, absolute reticulocyte count
 - Clinical chemistry: sodium, potassium, creatinine, chloride, calcium, BUN, bicarbonate, albumin, LDH, AST, ALT, ALP, glucose, total bilirubin, indirect bilirubin
 - FVIII inhibitor titer
 - FVIII:C in vivo recovery (Note: If FVIII:C in vivo recovery is ≥66%, separate visits must be scheduled at which time the assessment of FVIII:C half-life will be performed.)
 - Virus safety retain samples
 - Urinalysis: pH, protein, glucose, ketones, bilirubin, nitrites, urobilinogen, blood, leukocyte esterase (with microscopic examination of urine sediment if abnormal)
- Collect unused Alphanate

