5.1.3 Efficacy Analyses

Efficacy data and analyses will be performed on the Treated Population. As a sensitivity analysis, the analysis of the primary efficacy endpoint will also be performed on the Efficacy Evaluable Population.

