5.1.3.1 Analysis of Primary Efficacy Endpoint

The primary efficacy endpoint is the proportion of subjects achieving complete immune tolerance during the ITI Treatment Phase and will be compared to the historical spontaneous remission rate of 10%.

The proportion of subjects achieving complete immune tolerance receiving Alphanate during the ITI Treatment Phase will be calculated along with the 95% confidence interval (CI). The exact (Clopper-Pearson) method for the binomial proportion will be used to calculate the 95% CI (21). If the lower bound of the 95% CI is greater than 10%, then it is statistically significant that the proportion of subjects achieving complete immune tolerance receiving Alphanate is greater than the historical spontaneous remission rate of 10%.

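### Does the Efficacy Evaluable sensitivity analysis need changing because it may drop early withdrawals and keep every success?

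*Combined protocol and SAP*

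**What the plan says.** Section 5.1.3 places all efficacy analyses on the Treated Population, meaning everyone given at least one dose. It then adds: "As a sensitivity analysis, the analysis of the primary efficacy endpoint will also be performed on the Efficacy Evaluable Population". Section 5.1.3.1 gives the decision rule, based on the exact Clopper-Pearson interval: "If the lower bound of the 95% CI is greater than 10%, then it is statistically significant". Section 5.1.1 says that the EE Population "includes all subjects who were determined to have achieved complete immune tolerance, to have achieved partial immune tolerance", or to be treatment failures, so it admits only subjects placed in one of three response categories under the protocol's own definitions.

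Those definitions are in Section 3.5.1.2, where treatment failure is "Failure to fulfill the criteria for complete or partial immune tolerance within 33 months". Other sections tie failure to a date or list withdrawals separately:

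- Section 3.1: subjects who have not reached partial "immune tolerance at the completion of 33 months of ITI treatment will be discontinued as treatment failures".
- Section 3.9, among the reasons for mandatory removal: "Subject is determined to be a treatment failure at the completion of 33 months of ITI treatment".
- Section 3.6.4.8 describes the Early Termination Visit as being for "subjects who are withdrawn from the study for treatment failure or subjects who discontinue the study prematurely for any reason".
- Section 3.6.3.1 lists a virus sample "At the Early Termination Visit for treatment failures and early withdrawals".

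Section 5.1 leaves data handling to a Statistical Analysis Plan, whose text is not in the document reviewed.

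**The concern.** Complete tolerance can be confirmed at any time during the 33 months. Under Sections 3.1 and 3.9, failure is declared only at the end. A subject who withdraws at, say, Month 14 with no determined response then fits no category and leaves the EE denominator, while no success ever leaves it. The EE rate therefore equals or exceeds the Treated rate.

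This is the only sensitivity analysis the protocol names for the primary endpoint. On this reading it cannot challenge a positive primary result, and it could put a nominally significant figure beside a narrowly missed one. On the literal reading of Section 3.5.1.2, every withdrawal is a failure, EE equals Treated, and the analysis adds nothing. Either way it looks like a poor robustness check, with the 10% rule carried over to it.

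**Working it through.** **Inputs.** N = 25, null rate 10%, assumed rate 35%, one-sided alpha 0.025 (Section 5.2); Clopper-Pearson interval and 10% rule (Section 5.1.3.1). The documents give no withdrawal rate, so the share withdrawing without a determined response, w, is assumed to be 10%, 20%, 30% or 40%.

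**The plan's own figure.** The lower limit for x of n is the 2.5% quantile of Beta(x, n − x + 1). For 6/25 it is 9.36% and for 7/25 it is 12.07%, so the primary analysis needs at least 7 successes. P(X ≥ 7) is 0.95% at a true 10% and 82.7% at 35%. With 24 subjects the power is 78.9%. Twenty-five therefore supports the stated 80%, on the Treated Population.

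**How many exclusions cross the line.**

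| Successes | Treated lower limit | Last failing EE count | First passing EE count |
|---|---|---|---|
| 5 | 5/25: 6.83% | 5/18: 9.69% | 5/17: 10.31% (8 excluded) |
| 6 | 6/25: 9.36% | 6/24: 9.77% | 6/23: 10.23% (2 excluded) |
| 7 | 7/25: 12.07% | none | passes already |

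**How often it happens.** Each subject is an observed success (probability s), a kept non-success (f) or undetermined (1 − s − f). The rule is applied to successes/(successes + kept non-successes), summed exactly over all trinomial outcomes for N = 25. The success rate within EE is s/(s + f). At a true rate of 10%:

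- *Only non-responders leave:* s = 0.10, f = 0.90 − w.
- *Random, spread over time* (success times uniform over 3–33 months, exponential withdrawal reaching w by Month 33): s = 0.0945/0.0887/0.0827/0.0764; undetermined 0.0955/0.1913/0.2873/0.3836.
- *Random, before any success:* s = 0.10(1 − w), f = 0.90(1 − w).

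| w | Non-responders only: EE rate; EE passes | Random over time: EE passes | Random before any success: EE rate; EE passes |
|---|---|---|---|
| 10% | 11.1%; 2.5% | 1.9% | 10.0%; 1.5% |
| 20% | 12.5%; 3.6% | 2.1% | 10.0%; 1.3% |
| 30% | 14.3%; 5.5% | 2.4% | 10.0%; 1.3% |
| 40% | 16.7%; 8.5% | 2.9% | 10.0%; 1.2% |

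The upward bias is therefore conditional. It appears when withdrawal follows poor response, or when successes are confirmed before those subjects would have withdrawn. It is absent in the last column, where the Treated rate is the one pulled down, to 0.10(1 − w). At a true 20% with random withdrawal over time, the mean EE rate is 20.8/21.7/22.8/24.1% and the mean Treated rate 18.9/17.7/16.5/15.3%: similar errors in opposite directions.

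**Would the obvious substitute do better?** The natural candidate is the Month-33 Kaplan-Meier proportion, from a curve already planned in Section 5.1.3.2.

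- It cannot fall below the Treated rate either.
- At a true 20%, if 20% of subjects leave in the first 12 months and all are non-responders, it averages 24.5%, against 25.0% for EE.
- At a true 10% with random withdrawal over time, its log-log lower limit exceeds 10% in 3.1/3.7/4.3/3.9% of trials, more often than EE (1.9/2.1/2.4/2.9%).
- With 6 successes and withdrawals only after the last, S = 19/25 = 0.76, −ln S = 0.2744 and the standard error is √(0.76 × 0.24/25) = 0.0854. On the log-log scale this is 0.0854/(0.76 × 0.2744) = 0.4095. The lower limit is 1 − exp(−0.2744 × e^(−1.96 × 0.4095)) = 11.6%, where the exact 6/25 interval gives 9.36%.

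**The case for a change.** The best case for a change is that it costs a few sentences. In a 25-subject single-arm trial the result turns on six against seven successes, and two exclusions are enough to carry six over the line. Withdrawal linked to poor response is plausible: Section 3.9 allows removal at the family's request, on the investigator's judgement or for noncompliance, over 33 months of daily infusions. The passages that separate withdrawals from failures make exclusion the more natural reading.

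Much of this stands. Section 5.1.1 is silent, the exclusion reading is better supported, and an EE rate that cannot fall below the Treated rate is no stress test of a positive result.

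The remedies gain little, however. Counting withdrawals without complete tolerance as non-successes is already implied by taking a proportion of the Treated Population; the synopsis calls it an intent-to-treat analysis. Removing the 10% rule from EE while still printing its 95% interval leaves the same comparison in view, because the rule is simply the lower limit of that interval. Kaplan-Meier shares the weakness and crosses 10% more often under random withdrawal.

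The largest figure, 8.5%, also needs 40% of all subjects to leave, all of them non-responders and all undetermined. The Early Termination Visit collects inhibitor titer and recovery, and half-life when recovery is at least 66%, so some withdrawals may be classed as partial responders and stay in EE as non-successes. If half of the 40% were classed, the figure would be the 20% row, 3.6%.

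**Conclusion.** No change to the plan follows. The omission is real but is a point of data handling that Section 5.1 assigns to the SAP, and analysts can settle it with either classing without touching the primary result. That result rests on at least 7 of 25 in the Treated Population, with 0.95% type I error and 82.7% power at 35%. No section lets the EE result stand in for it.

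The possible distortion is confined to an analysis labelled as sensitivity. Under the exclusion reading, at a true 10%, the EE analysis passes in 1.2% to 8.5% of trials across the scenarios shown, and exceeds 2.5% only when withdrawal tracks poor response or, if random over time, at 40%. Under the literal reading of Section 3.5.1.2 the distortion is nil. These figures rest on assumed withdrawal rates and timing, since the documents give none, and on the SAP's classing rule not having been seen. A reader of the eventual report should treat EE as supportive and take the 10% decision from the Treated Population, as the plan already provides.
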